3.2.7 Organ Function Requirements

3.2.7.1 Adequate Bone Marrow Function Defined As:

- Peripheral absolute neutrophil count (ANC) $\geq 1000/\mu\text{L}$
- Platelet count $\geq 100,000/\mu\text{L}$ (transfusion independent)
- Hemoglobin $\geq 8.0 \text{ g/dL}$ (may receive RBC transfusions)

3.2.7.2 Adequate Renal Function Defined As:

- Creatinine clearance or radioisotope GFR $\geq 70 \text{ mL/min}/1.73 \text{ m}^2$ **or**
- A serum creatinine based on age/gender as follows:

Age	Maximum Serum Creatinine (mg/dL)	
	Male	Female
1 month to < 6 months	0.4	0.4
6 months to < 1 year	0.5	0.5
1 to < 2 years	0.6	0.6
2 to < 6 years	0.8	0.8
6 to < 10 years	1	1
10 to < 13 years	1.2	1.2
13 to < 16 years	1.5	1.4
$\geq 16 \text{ years}$	1.7	1.4

The threshold creatinine values in this Table were derived from the Schwartz formula for estimating GFR (Schwartz et al. J. Pediatr., 106:522, 1985) utilizing child length and stature data published by the CDC.

3.2.7.3 Adequate Liver Function Defined As:

- Total bilirubin $\leq 1.5 \times$ upper limit of normal (ULN) for age, and
- SGPT (ALT) $\leq 110 \text{ U/L}$. For the purpose of this study, the ULN for SGPT is 45 U/L.
- Serum albumin $\geq 2 \text{ g/dL}$.

3.2.7.4 Adequate Pulmonary Function Defined As:

- No evidence of dyspnea at rest and a pulse oximetry $> 94\%$ if there is clinical indication for determination.

3.2.8 Patients must be able to swallow intact capsules.

EXCLUSION CRITERIA

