- confirmation of negative serum or urine pregnancy test (sensitivity of at least 25 mIU/mL) in female patients of childbearing potential,
- confirmation of the use of 2 forms of effective birth control for female patients of childbearing potential OR confirmation of commitment to complete abstinence, and
- completion and documentation of required lenalidomide education and counseling (all patients)

Dose calculations should be based on actual BSA and adjusted as necessary prior to each cycle. There is no maximum dosing.

Lenalidomide: PO once daily

Days: 1 through 21.

Dose: Regimen A (Low Dose): 20 mg/m²/dose (See [Appendix X](#) for Dosing Tables)
Regimen B (High Dose): 115 mg/m²/dose

Note: The calculated dose should be rounded to within 10% of the prescribed dose for convenience of capsule size. The calculated dose should be rounded in a manner to minimize the daily number of capsules. The dose should be given without food when possible, although this is not mandatory. If a patient vomits a dose within 10 minutes of administration and the capsules are clearly visible, the dose may be repeated. The capsules should be swallowed whole and not opened or chewed.

See [Section 5.0](#) for Dose Modifications based on Toxicities.

The therapy delivery maps (TDMs) for this cycle are on the next two pages. See [Section 4.3.1](#) for the Regimen A (Low Dose: 20 mg/m²/dose) therapy delivery map and [Section 4.3.2](#) for the Regimen B (High Dose: 115 mg/m²/dose) therapy delivery map.

Following completion of the first cycle, the lenalidomide cycle is repeated for up to a total of 26 cycles, as tolerated and in the absence of disease progression (see [Section 10.4](#) for Response Evaluation). If disease progression occurs, the patient will be taken off protocol therapy.

Susbequent lenalidomide cycles should begin on Day 29 or when ANC \geq 1,000/ μ L, platelet count \geq 100,000/ μ L (transfusion independent), whichever occurs later, AND once the following criteria have been met:

- confirmation of negative serum or urine pregnancy test (sensitivity of at least 25 mIU/mL),
- confirmation of the use of 2 effective methods of birth control for female patients of childbearing potential OR confirmation of commitment to complete abstinence,
- completion and documentation of required lenalidomide education and counseling (all patients).

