4.3.1 Lenalidomide Cycle – Regimen A (Low Dose: 20 mg/m²)

Four consecutive weeks (28 days) will constitute one cycle (Lenalidomide daily x 21 days followed by 7 day rest). This therapy delivery map relates to all cycles of Regimen A. Use a copy of this page once for each cycle. (Please note cycle number below.)

Patient name or initials

DOB

Criteria to start this cycle: ANC \geq 1,000/ μ L and platelet count \geq 100,000/ μ L (transfusion independent), confirmation of negative pregnancy test and the use of 2 methods of effective birth control for female patients of childbearing potential or commitment to complete abstinence, completion and documentation of required counseling. Details are in [Section 4.0](#) (Treatment Overview). The Therapy Delivery Map for this cycle is on 1 page.

DRUG	ROUTE	DOSAGE	DAYS	IMPORTANT NOTES	OBSERVATIONS
Lenalidomide NSC#703813	PO	20 mg/m ² /dose	1-21	See admin guidelines in Section 4.3 . (See Appendix IX for Dosing Tables)	
 a. History, PE (Ht, Wt, VS), Performance Status b. CBC (differential, platelets) c. Urinalysis d. Electrolytes (inc BUN, Calcium, PO₄, Magnesium) e. Creatinine; Total protein; Albumin, ALT, AST, bilirubin f. Pregnancy test (female pts of childbearing potential only) g. Brain MRI with and without gadolinium h. Spine MRI with and without gadolinium i. Pharmacokinetic study (see Section 13.0) j. Required Education and Counseling; Confirmation of birth control/abstinence 
OBTAINT OTHER STUDIES AS REQUIRED FOR GOOD PATIENT CARE

Please Enter Cycle #: _____ Ht _____ cm Wt _____ kg BSA _____ m²

Date Due	Date Given	Day	Lenalidomide mg	Studies	Comments (Include any held doses, or dose modifications)	
Enter calculated dose above and actual dose administered below						
		1	mg	a, b [@] , c, d, e, f*, g [#] , h [^] , j		
		2	mg			
		3	mg			
		4	mg			
		5	mg	i ^{\$}		
		6	mg			
		7	mg			
		8	mg	b, d, f*		
		9	mg			
		10	mg			
		11	mg			
		12	mg			
		13	mg			
		14	mg			
		15	mg	b, d, f*		
		16	mg			
		17	mg			
		18	mg			
		19	mg			
		20	mg			
		21	mg	b, d, f*		
		29	Start next cycle on Day 29 or when blood count parameters are met (whichever occurs later). For end of therapy observations, see Section 7.1 .			

[@]Obtain weekly. If patient develops hematologic toxicity as defined in [Section 5.2](#), CBCs should be checked every 3 to 4 days until recovery to Grade 3.

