Lenalidomide binding to plasma proteins is low with mean plasma protein binding around 30% (22.7% and 29.2% in multiple myeloma patients and healthy volunteers, respectively). Lenalidomide is neither metabolized by nor inhibited or induced by the cytochrome P450 pathway. In healthy volunteers, lenalidomide undergoes limited metabolism and the parent compound is the predominant circulating component. Approximately 65% to 85% of lenalidomide is eliminated unchanged in the urine. The half-life of elimination is approximately 3 hours at the clinically relevant doses and steady-state levels are achieved within 4 days. Pharmacokinetic analyses in patients with impaired renal function indicate that as renal function decreases, the total drug clearance decreases proportionally resulting in an increase in AUC. The half-life of lenalidomide increased from approximately 3.5 hours in subjects with creatinine clearance > 50 mL/min to more than 9 hours in subjects with creatinine clearance < 50 mL/min; therefore, patients with inadequate renal function are ineligible for this study.

With regards to potential drug interactions, the periodic monitoring of digoxin plasma levels is recommended due to increased Cmax with concomitant administration of lenalidomide. Patients taking concomitant therapies such as erythropoietin stimulating agents or estrogen containing therapies may have an increased risk of venous thromboembolic events. Therefore, erythropoietic agents should not be used while patients are receiving lenalidomide on this trial. Other agents that may increase the risk of thrombosis, such as estrogen containing therapies, should be used with caution in patients receiving lenalidomide.

Toxicity:

Comprehensive Adverse Events and Potential Risks list (CAEPR) for Lenalidomide (CC-5013, NSC 703813)

The Comprehensive Adverse Events and Potential Risks list (CAEPR) provides a single list of reported and/or potential adverse events (AE) associated with an agent using a uniform presentation of events by body system. In addition to the comprehensive list, a subset, the Specific Protocol Exceptions to Expedited Reporting (SPEER), appears in a separate column and is identified with bold and italicized text. This subset of AEs (SPEER) is a list of events that are protocol specific exceptions to expedited reporting to NCI (except as noted below). Refer to the 'CTEP, NCI Guidelines: Adverse Event Reporting Requirements'

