7.1 Required Clinical, Laboratory and Disease Evaluations

All baseline studies must be performed prior to starting protocol therapy unless otherwise indicated below. **Obtain other studies prior to start of subsequent cycles and as otherwise indicated.**

STUDIES TO BE OBTAINED	Baseline	Prior to Each Cycle	During Each Cycle	When Patient is Removed from Protocol Therapy
History	X	X		
Physical Exam (Ht, Wt, VS)	X	X		X
Performance Status	X	X		X
CBC (differential, platelets)	X	X	Weekly ^A	X
Urinalysis	X	X		X
Electrolytes (including BUN, Calcium, PO ₄ , Magnesium)	X	X	Weekly	X
Creatinine	X	X		
Total protein, AST, ALT, albumin, bilirubin	X	X		X
Pregnancy test (serum or urine, with sensitivity of 25 mIU/mL) (for females of childbearing potential)	X ^B	X ^B	Weekly ^C	X ^D
Confirmation of use of 2 effective methods of birth control OR confirmation of complete abstinence (for female patients of childbearing potential)	X	X		
Education and Counseling (all patients) ^E		X		X
Brain MRI with and without gadolinium	X ^F	X ^G		X
Spine MRI with and without gadolinium ^{F,H}	X	X ^G		X
Pharmacokinetic studies (see Section 13.0)			X ^I	

^A If patient develops hematologic toxicity as defined in [Section 5.2](#), CBCs should be checked every 3 to 4 days until recovery.

^B Obtain 2 weeks prior to study enrollment and again within 24 hours prior to Day 1 of each cycle.

^C Obtain weekly during cycle 1. Females with irregular menstruation must have a pregnancy test every 14 days while receiving protocol therapy (including breaks in treatment). Pregnancy test is also required if patient misses her period or has unusual menstrual bleeding.

^D Pregnancy testing must also occur at Day 28 (and at Day 14 if female has irregular menstruation) after lenalidomide discontinuation.

^E The Lenalidomide Education and Counseling Document ([Appendix III](#)) must be completed and signed by a trained counselor at the site prior to each dispensing of lenalidomide.

^F Obtain brain MRI within 1 week prior to study enrollment. Spine MRI (if necessary) may be obtained within 2 weeks prior to enrollment.

^G Obtain prior to each odd-numbered cycle of therapy (ie, prior to cycles 3, 5, 7, 9, 11 and 13) for the first 13 cycles. During cycles 14-26, imaging will be performed every third cycle (ie, prior to

16, 19, 22 and 25), after cycle 26, and as clinically indicated. See [Section 14.0](#) for imaging requirements.

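### Renal function limits entry because of drug exposure, and creatinine is drawn before every cycle, but the criteria for starting cycles 2 to 26 contain no renal value

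*Combined protocol and SAP*

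**What the plan says.** Section 6.1 gives the pharmacology. "Approximately 65% to 85% of lenalidomide is eliminated unchanged in the urine", and "as renal function decreases, the total drug clearance decreases proportionally resulting in an increase in AUC". It continues: "The half-life of lenalidomide increased from approximately 3.5 hours in subjects with creatinine clearance" above 50 mL/min to more than 9 hours below that value; "therefore, patients with inadequate renal function are ineligible for this study".

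Section 3.2.7.2 turns this into an entry rule: "Creatinine clearance or radioisotope GFR" of at least 70 mL/min/1.73 m², or a serum creatinine no higher than a tabulated limit for age and sex.

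Section 7.1 marks creatinine at baseline and before each cycle ("Obtain other studies prior to start of subsequent cycles and as otherwise indicated"). Both therapy delivery maps (4.3.1 and 4.3.2) list it on Day 1 of every cycle.

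For later cycles, Section 4.3 states "Susbequent lenalidomide cycles should begin on Day 29 or when ANC" and platelets reach 1,000/µL and 100,000/µL. It also requires a negative pregnancy test, confirmed contraception or abstinence, and documented counseling. The start criteria on each map give the same items, and the Day 29 line on each map reads "Start next cycle on Day 29 or when blood count parameters are met (whichever occurs later". No renal value appears in any of them. Therapy may run to 26 cycles.

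**The concern.** The reason for the entry limit is exposure, and it applies at cycle 10 as much as at cycle 1. Cycle 1 is covered: eligibility tests fall within 7 days before enrollment, and treatment is due to start within 5 days after it. Later cycles have no equivalent. A child whose renal function has dropped below the entry limit would have that recorded on Day 1, and the start criteria would still be met.

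This matters most for Regimen B. Section 2.4 describes its starting dose of 115 mg/m² as the top dose evaluated in the pediatric CNS phase I study (PBTC-018, 15 to 116 mg/m²/day), so there is almost no tested dose range above it. What is at stake is patient safety; no effect on the response endpoint is argued.

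**Working it through.** **Step 1. Where a renal value is used.**

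| Place | Renal value |
|---|---|
| 3.2.7.2, entry | Limit set: GFR at least 70, or creatinine by age and sex |
| 7.1 and both delivery maps | Creatinine measured before each cycle; no action limit |
| 4.3 and both maps, start of later cycles | None |
| 5.1, non-hematologic toxicity | Not named; acts on listed triggers at least possibly attributed to lenalidomide |
| 5.2, hematologic toxicity | None; acts on counts, platelet transfusions and count-related delays |
| 8.1, removal from therapy | None; item (e) leaves it to the physician |

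The entry limit is therefore not carried forward, although the test it needs is already scheduled.

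**Step 2. Size of the exposure change.** The plan states no figure for this, so there is nothing to reproduce. Take a GFR falling from 70 (the entry floor) to 50 (the value at which 6.1 splits its half-life data).

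- Renal share model: AUC ratio = 1 / (1 − fe × (1 − 50/70)), where fe is the share eliminated unchanged in urine (0.65 to 0.85, Section 6.1).
  - fe = 0.65: 1 / (1 − 0.65 × 0.2857) = 1 / 0.8143 = 1.23
  - fe = 0.85: 1 / (1 − 0.85 × 0.2857) = 1 / 0.7571 = 1.32
- Total clearance proportional to GFR, as 6.1 words it: 70/50 = 1.40

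**Step 3. Dose equivalents.** Sections 2.4 and 6.1 both report that AUC is linear in dose, so an AUC ratio converts to a dose in the same patient.

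- Regimen B: 115 × 1.228 = 141; 115 × 1.321 = 152; 115 × 1.40 = 161 mg/m². Against 116 mg/m², that is 141/116 = 1.22 to 161/116 = 1.39 times the highest phase I dose.
- Regimen A: 20 × 1.228 = 25 to 20 × 1.40 = 28 mg/m², inside the tested range.

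**Step 4. What the half-life figures would imply.** With volume and absorption unchanged, 9/3.5 = 2.57 times the AUC, or 115 × 2.571 = 296 mg/m². To reach 2.57, the models of Step 2 need GFR to fall to this share of baseline:

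- fe = 0.65: 1 − (1 − 1/2.571)/0.65 = 0.06
- fe = 0.85: 1 − (1 − 1/2.571)/0.85 = 0.28
- proportional clearance: 1/2.571 = 0.39

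From a baseline of 70 that is a GFR of about 4 to 27, which is severe impairment.

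**The case against.** The strongest reply is that the protocol is not silent on a child whose kidneys are failing.

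- CBC is checked weekly, counts control the start of every cycle, and the Section 5.2 reductions need no attribution. Myelosuppression was the primary toxicity in the phase I study, so excess exposure that produced it would meet a rule.
- BUN is drawn weekly with the electrolytes, and urinalysis is done before each cycle.
- Section 5.1 needs only possible attribution, and the Section 6.1 adverse event list includes acute kidney injury as a rare but serious possible effect.
- Later cycles are given subject to tolerance, Section 5.1 foresees delays for non-hematologic toxicity, and Section 8.1(e) allows removal.

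All of this stands, and it narrows the gap without closing it. Section 5.2 acts only after marrow toxicity, and because Section 5.0 forbids re-escalation, a reversible renal dip could then cost the child a permanent reduction. BUN has no action limit. The Section 6.1 list also places raised creatinine among events with insufficient evidence of a causal link, so a site could reasonably judge a moderate rise unrelated. What remains is discretion without a threshold.

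Two further points are fair. Pharmacokinetic samples are taken only in cycle 1 and after a dose reduction, but they are correlative and do not guide dosing, so their absence later removes no safety rule. The statement that there is no maximum dose concerns scaling by body surface area and does not change the mg/m² dose.

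**Conclusion.** The point holds as a low-cost safety improvement. The start criteria for cycles 2 to 26 omit a limit that the protocol justifies on exposure grounds and already collects the data to apply. For a fall in GFR from 70 to 50, Regimen B would act like 141 to 161 mg/m² in the same patient.

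That range assumes a baseline at the entry floor, clearance that follows one of the two models above, and linear pharmacokinetics. The match to Section 6.1 is approximate, because its cut-off is in mL/min while the entry limit is per 1.73 m².

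A reader might infer more, and the documents do not support it:

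- That exposure would rise 2.57 times. This needs severe renal impairment and does not describe a child who has drifted past the entry limit.
- That exposure would exceed anything seen in phase I. The comparison is with the highest dose. No phase I AUC range is given, and a patient with low clearance there may have had a similar AUC.
- That harm has been shown. No MTD was reached. Section 2.4 calls it unclear whether myelosuppression is dose-related, while noting a possible trend at 68 mg/m²/day and above.
- That a known number of the 37 planned Regimen B patients would be affected. No rate of on-study renal decline is given.

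**What to change.** Add one criterion for later cycles to Section 4.3 and to the start criteria on both delivery maps, and bring the Day 29 line into agreement: *serum creatinine within the Section 3.2.7.2 limit for age and sex, or creatinine clearance or radioisotope GFR at least 70 mL/min/1.73 m²; otherwise hold lenalidomide and repeat.* This reapplies the entry standard and is no stricter than it.

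Add one clause to Section 5.1: a renal hold not attributed to lenalidomide does not trigger a dose reduction. If the sponsor also wants a maximum length of hold, that needs a line in Section 8.1.

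The cost is a few lines of text and no new routine test. Some cycles would be delayed, and some patients over the creatinine limit would need a confirmatory clearance or GFR test. Sample size and error rates do not change.

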4.3.1 Lenalidomide Cycle – Regimen A (Low Dose: 20 mg/m²)

Four consecutive weeks (28 days) will constitute one cycle (Lenalidomide daily x 21 days followed by 7 day rest). This therapy delivery map relates to all cycles of Regimen A. Use a copy of this page once for each cycle. (Please note cycle number below.)

Patient name or initials

DOB

Criteria to start this cycle: ANC \geq 1,000/ μ L and platelet count \geq 100,000/ μ L (transfusion independent), confirmation of negative pregnancy test and the use of 2 methods of effective birth control for female patients of childbearing potential or commitment to complete abstinence, completion and documentation of required counseling. Details are in [Section 4.0](#) (Treatment Overview). The Therapy Delivery Map for this cycle is on 1 page.

DRUG	ROUTE	DOSAGE	DAYS	IMPORTANT NOTES	OBSERVATIONS
Lenalidomide NSC#703813	PO	20 mg/m ² /dose	1-21	See admin guidelines in Section 4.3 . (See Appendix IX for Dosing Tables)	
 a. History, PE (Ht, Wt, VS), Performance Status b. CBC (differential, platelets) c. Urinalysis d. Electrolytes (inc BUN, Calcium, PO₄, Magnesium) e. Creatinine; Total protein; Albumin, ALT, AST, bilirubin f. Pregnancy test (female pts of childbearing potential only) g. Brain MRI with and without gadolinium h. Spine MRI with and without gadolinium i. Pharmacokinetic study (see Section 13.0) j. Required Education and Counseling; Confirmation of birth control/abstinence 
OBTAINT OTHER STUDIES AS REQUIRED FOR GOOD PATIENT CARE

Please Enter Cycle #: _____ Ht _____ cm Wt _____ kg BSA _____ m²

Date Due	Date Given	Day	Lenalidomide mg	Studies	Comments (Include any held doses, or dose modifications)	
Enter calculated dose above and actual dose administered below						
		1	mg	a, b [@] , c, d, e, f*, g [#] , h [^] , j		
		2	mg			
		3	mg			
		4	mg			
		5	mg	i ^{\$}		
		6	mg			
		7	mg			
		8	mg	b, d, f*		
		9	mg			
		10	mg			
		11	mg			
		12	mg			
		13	mg			
		14	mg			
		15	mg	b, d, f*		
		16	mg			
		17	mg			
		18	mg			
		19	mg			
		20	mg			
		21	mg	b, d, f*		
		29	Start next cycle on Day 29 or when blood count parameters are met (whichever occurs later). For end of therapy observations, see Section 7.1 .			

[@]Obtain weekly. If patient develops hematologic toxicity as defined in [Section 5.2](#), CBCs should be checked every 3 to 4 days until recovery to Grade 3.

[#]Obtain within 24 hours prior to starting each cycle and weekly during cycle 1. If menstrual cycles are known to be irregular, pregnancy testing must occur every 14 days beginning with Day 1 of Cycle 2. If a patient misses her period or menstrual bleeding becomes irregular, hold lenalidomide and perform pregnancy testing and counseling immediately. Only for females of childbearing potential.

^{\$}Obtain prior to each odd-numbered cycle of therapy (ie, prior to cycles 3, 5, 7, 9, 11 and 13) for the first 13 cycles. During cycles 14-26, obtain every third cycle (ie, prior to cycles 16, 19, 22 and 25), after cycle 26 and as clinically indicated.

[^]Obtain at same time points as brain MRI, for patients with known or suspected spinal disease.

\$ For PK study, obtain 2 mL blood in heparinized tube (green top) any day between Days 5-21 of Cycle 1 and any day between Days 5-21 of the first cycle following a dose reduction at the time of safety lab monitoring. See [Section 13.0](#).

See [Section 5.0](#) for Dose Modifications for Toxicities. For COG Supportive Care Guidelines see: https://members.childrensoncologygroup.org/prot/reference_materials.asp.

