4.3.2 Lenalidomide Cycle – Regimen B (High Dose: 115 mg/m²)

Four consecutive weeks (28 days) will constitute one cycle (Lenalidomide daily x 21 days followed by 7 day rest). This therapy delivery map relates to all cycles of Regimen B. Use a copy of this page once for each cycle. (Please note cycle number below.)

Patient name or initials

DOB

Criteria to start this cycle: ANC \geq 1,000/ μ L and platelet count \geq 100,000/ μ L (transfusion independent), confirmation of negative pregnancy test and the use of 2 methods of effective birth control for female patients of childbearing potential or commitment to complete abstinence, completion and documentation of required counseling. Details are in [Section 4.0](#) (Treatment Overview). The Therapy Delivery Map for this cycle is on 1 page.

DRUG	ROUTE	DOSAGE	DAYS	IMPORTANT NOTES	OBSERVATIONS
Lenalidomide NSC#703813	PO	115 mg/m ² /dose	1-21	See admin guidelines in Section 4.3 .	
 a. History, PE (Ht, Wt, VS), Performance Status b. CBC (differential, platelets) c. Urinalysis d. Electrolytes (inc BUN, Calcium, PO₄, Magnesium) e. Creatinine; Total protein; Albumin, ALT, AST, bilirubin f. Pregnancy test (female pts of childbearing potential only) g. Brain MRI with and without gadolinium h. Spine MRI with and without gadolinium i. Pharmacokinetic study (see Section 13.0) j. Required Education and Counseling; Confirmation of birth control/abstinence 
OBTAINT OTHER STUDIES AS REQUIRED FOR GOOD PATIENT CARE

Please Enter Cycle #: _____

Ht _____ cm

Wt _____ kg

BSA _____ m²

Date Due	Date Given	Day	Lenalidomide mg	Studies	Comments (Include any held doses, or dose modifications)	
Enter calculated dose above and actual dose administered below						
		1	mg	a, b [@] , c, d, e, f*, g [#] , h [^] , j		
		2	mg			
		3	mg			
		4	mg			
		5	mg	i ^{\$}		
		6	mg			
		7	mg			
		8	mg	b, d, f*		
		9	mg			
		10	mg			
		11	mg			
		12	mg			
		13	mg			
		14	mg			
		15	mg	b, d, f*		
		16	mg			
		17	mg			
		18	mg			
		19	mg			
		20	mg			
		21	mg	b, d, f*		
		29	Start next cycle on Day 29 or when blood count parameters are met (whichever occurs later). For end of therapy observations, see Section 7.1 .			

[@] Obtain weekly. If patient develops hematologic toxicity as defined in [Section 5.2](#), CBCs should be checked every 3 to 4 days until recovery to grade 3.

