5.2 Hematologic Toxicities

The dose of lenalidomide will be reduced for any of the following toxicities:

- Grade 4 decreased neutrophil count (neutropenia) > 3 days duration
- Grade 4 decreased platelet count (thrombocytopenia)

- ≥ 2 platelet transfusions per cycle for platelet counts $< 50,000/\mu\text{L}$
- ≥ 14 day delay in starting subsequent cycles due to low ANC ($< 1,000/\mu\text{L}$ or low platelet count ($< 100,000/\mu\text{L}$).
- If ANC $< 500/\mu\text{L}$ and platelets $< 100,000/\mu\text{L}$ during the 21 day dosing period, the lenalidomide should be held until recovery. Counting of cycle days should continue uninterrupted.

Patients who experience hematologic toxicity should have appropriate laboratory testing at least twice weekly (3-4 days apart) until the toxicity has resolved (i.e. ANC $> 1000/\mu\text{L}$ and platelets $> 100,000/\mu\text{L}$).

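### Both therapy delivery maps stop the 3-4 day CBC checks at recovery to Grade 3, short of the ANC and platelet thresholds that Section 5.2 requires

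*Combined protocol and SAP*

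**What the plan says.** Each delivery map sets CBCs weekly and carries a footnote for patients who develop hematologic toxicity as defined in Section 5.2.

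- Section 4.3.1 (Regimen A): "CBCs should be checked every 3 to 4 days until recovery to Grade 3".
- Section 4.3.2 (Regimen B): "CBCs should be checked every 3 to 4 days until recovery to grade 3".
- Section 5.2: such patients "should have appropriate laboratory testing at least twice weekly (3-4 days apart) until the toxicity has resolved". Resolution is spelled out as ANC above 1000/µL and platelets above 100,000/µL.
- Section 7.1, footnote A: checks every 3 to 4 days until recovery, with a pointer to Section 5.2 for the trigger but no threshold of its own.

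The map is the working page for the site: "Use a copy of this page once for each cycle". Treatment can run to 26 cycles.

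Section 5.2 lists five bullets. Two are defined by Grade 4: neutropenia lasting more than 3 days, and thrombocytopenia. Two others are listed separately: two or more "platelet transfusions per cycle for platelet counts" below 50,000/µL, and a delay of at least 14 days, described as "14 day delay in starting subsequent cycles due to low ANC" (below 1,000/µL) or low platelets (below 100,000/µL). The fifth covers holding the drug during the dosing period.

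**The concern.** The map footnote takes its trigger from Section 5.2 and uses the same 3-4 day interval, but then prints a different stop point. No section says which governs. A coordinator working from the map has no reason to look further, because the footnote reads as a complete instruction.

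Grade 3 is not treated as resolved elsewhere in the protocol. Section 9.8 records Grade 3 or greater hematologic toxicity and compares it between doses, and Section 11.10 makes Grade 3 and higher events routinely reportable.

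What is at stake is how closely a child with an unresolved cytopenia is watched. Section 2.4 names myelosuppression as the primary toxicity in the pediatric phase I CNS study. It reports a possible trend to more Grade 3 and 4 episodes at 68 mg/m²/day and above, and Regimen B gives 115 mg/m². The same section also says that myelosuppression was sporadic and not clearly associated with dose, and that no patient had Grade 4 myelosuppression in Course 1. This background makes the footnote relevant but does not show that many patients would reach it.

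**Working it through.** The plan gives no figure to reproduce. The check is a comparison of stop points, followed by a count of the visits at which the two rules differ.

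**Stop points side by side**

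| Place | Stop point |
|---|---|
| 4.3.1 and 4.3.2 map footnotes | Recovery to Grade 3 |
| 5.2 | ANC > 1000/µL and platelets > 100,000/µL |
| 7.1 footnote A | Recovery, no threshold |

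A patient who improves from Grade 4 to Grade 3 leaves 3-4 day testing under the map and stays on it under Section 5.2.

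**Triggers not defined by Grade 4.** A patient can reach two platelet transfusions, or a 14-day delay, without a Grade 4 count. The stop point may then be met when the toxicity is declared, and the map asks for no extra check. Section 5.2 still asks for twice-weekly testing.

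**Checks omitted after a Grade 4 count**

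Inputs from the maps: counts on Days 8, 15 and 21, and a count before the next cycle on Day 28/29. Assumptions: Section 5.2 checks fall 3 or 4 days after each map count, Grade 3 is reached at the first extra check, the toxicity stays unresolved to Day 29, and Grade 3 lies below the Section 5.2 thresholds (the protocol does not print the CTCAE limits).

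| Found | Extra checks under 5.2 | Extra checks under map | Omitted by map |
|---|---|---|---|
| Day 8 | 8+3/4 = 11/12; 15+3/4 = 18/19; 21+3/4 = 24/25 | 11/12 | 18/19 and 24/25: two |
| Day 15 | 18/19; 24/25 | 18/19 | 24/25: one |
| Day 21 | 24/25 | 24/25 | none |

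Day 18/19 lies in the 21-day dosing period. Day 24/25 lies in the rest week (Days 22-28). When the Day 24/25 check is omitted, the longest interval between counts is 28 − 21 = 7 to 29 − 21 = 8 days, against 3-4 days under Section 5.2.

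The Day 8 row fits Grade 4 thrombocytopenia, which has no duration requirement. It does not clearly fit neutropenia: Grade 4 on Day 8 and Grade 3 by Day 11/12 does not establish more than 3 days at Grade 4. For a trigger not defined by Grade 4, the first extra check could be missing as well; that is not counted in the table.

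**The case against.** The strongest reply is that nothing in the map waives Section 5.2. The footnote names that section, the map refers to Section 5.0 for dose modifications, and it asks for other studies as good care requires. Weekly counts continue, and the next cycle stays gated at ANC of at least 1,000/µL and platelets of at least 100,000/µL. All of this is true, and it is why the point is minor. It does not remove the conflict: the footnote cites Section 5.2 only for the trigger, and the gate governs retreatment, not how often an unresolved cytopenia is checked meanwhile.

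It can also be said that one of the two omitted checks falls in the drug-free week. That stands. A comparison sign missing before the grade cannot be excluded, but both maps read the same, which makes it unlikely.

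A reader might infer more than the documents support:

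- **Lost doses.** Because "Counting of cycle days should continue uninterrupted" during a hold, seeing recovery on Day 21 instead of Day 18/19 might seem to cost 2-3 of 21 doses. But the hold bullet requires ANC below 500/µL and platelets below 100,000/µL together, and it gives no threshold for the recovery that ends the hold. If the hold ends once its own condition clears, the loss may be zero.
- **Cycle delay.** Seeing recovery on Day 36 instead of Day 32/33 would be 3-4 days late, but this assumes weekly counts after Day 29. The documents set no such schedule for a delay; the cycle starts when the counts are met.
- **Missed dose reductions.** The Section 5.2 list is itself the dose-reduction list, so patients who trigger the footnote have generally already met a reduction criterion.

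**Conclusion.** The inconsistency is real, and both map footnotes are wrong as written. A site can comply with its map and fall short of Section 5.2. The size is small: up to about two omitted checks per cycle in an early-onset Grade 4 case, one in the dosing period and one in the rest week, and fewer or none when the toxicity is found later. This count rests on the visit days and recovery pattern assumed above and on Grade 3 lying below the Section 5.2 thresholds. The finding that the stop points differ needs none of those assumptions. The documents do not say how many patients would be affected. The point does not bear on the primary response analysis, the Section 9.8 comparison or the dose-reduction rules. It is a minor safety-monitoring correction, held with high confidence as to the wording and only conditionally as to the number of checks.

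**What to change.** In the CBC footnotes of both delivery maps (4.3.1 and 4.3.2), replace the Grade 3 stop point with: *until ANC > 1000/µL and platelets > 100,000/µL (Section 5.2)*. Adding the same threshold to footnote A of Section 7.1 is optional, for consistency, since that footnote already points to Section 5.2.

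The cost is a wording change in two footnotes, or three with the optional one. Sites that would have followed the map would draw about one extra CBC per week until resolution, which Section 5.2 already requires.
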